14. STATISTICAL CONSIDERATIONS AND METHODS

14.1. Determination of Sample Size

14.1.1. Efficacy

The primary endpoint for efficacy is cumulative morphine demand via NCA. To detect a difference in effect size of 0.9, 20 subjects for each group (active treatment group pooled across all age groups vs. placebo group pooled across all age groups) will have 80% power at 2-sided significance level of 0.05.

14.1.2. Pharmacokinetics

Earlier PK modeling indicated that the best fitting model was 2 compartmental and that the inter- and intra-subject coefficient of variation (CV[%]) for clearance and volume of distribution were 54% and 20%, respectively. If each subject provides 3 data points in the ranges of absorption and terminal elimination phases, the total CV(%) (combination of the inter- and intra-subject CV[%]) is approximately 60%. Based on this assumption, a total of 34 subjects are needed to provide estimates of clearance and volume of distribution if their 95% confidence interval (CI) is within the range of 0.6 to 1.4 of the point estimates with 90% power.

For the single-dose phase, 5 subjects from each age group will receive oxymorphone (up to 60 total subjects, depending on IDMC recommendations for each age group). For the multiple-dose phase, 10 subjects from each age group will be randomized to receive either oxymorphone or placebo (40 total subjects). This will provide up to 80 subjects that are evenly distributed over the 4 age groups for the final population PK modeling and analysis.

PK in this study will be characterized using population PK modeling and analysis. Blood samples collected from the single-dose phase will be based on a 4-hour dosing interval since this is the specified period for evaluation of the dose strength. Four (4) blood samples will be collected from each subject according to the randomized subject number. Subjects with even subject numbers will have blood samples collected at 0.5, 2, 3, and 4 hours after dosing. Subjects with odd subject numbers will have blood samples collected at 1, 2, 3, and 4 hours after dosing. A window of ± 10 minutes is allowed.

In the multiple-dose phase, PK blood samples will be collected just before each dose (ie, at each trough). Population PK analyses will be used to estimate the clearance from multiple trough samples collected in the same subject. The date/time and study drug dose, as well as the date/time of each sample collection, must be recorded accurately. However, no specific schedule needs to be followed other than that each sample be collected as a trough sample just before the next dose.

If any other source of oxymorphone is administered (including oxycodone, which has oxymorphone as a metabolite), no further PK samples will be collected.

The population PK modeling and analysis will pool the available data from both phases of this study to estimate the oral clearance and oral volume of distribution using age, weight, and other potential covariates.

14.2. Subject Populations

14.2.1. Analysis Populations

A population PK analysis will be performed using data from both single-dose and multiple-dose phases. The PK population will include all subjects who receive oxymorphone HCl (immediate-release oral liquid or IV formulation) and have plasma concentration data from at least 1 time point from either single-dose or multiple-dose phase to facilitate the population PK modeling and analysis.

14.2.1.1. Single-dose Phase

The safety population for the single-dose phase will include all subjects who receive at least 1 dose of study drug. All safety analyses and demographic/baseline characterization for the single-dose phase will be performed using this population.

The single-dose PK population will include all subjects who receive oxymorphone HCl (immediate-release oral liquid or IV formulation) and provide sufficient data points to facilitate the calculation for non-compartmental PK parameters.

The evaluable population will include all subjects who receive at least 1 dose of the study medication and provide a minimum of 4 hours of post-dose assessments and at least 3 PK assessments to facilitate the dose selection decision. All efficacy analyses for the single-dose phase will be performed on this population.

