8.3. Study Drug Administration

Study drug in the form of oral liquid will be provided for subjects in age groups A and B. If a subject in groups A or B does not consume the entire dose, the subject should not be redosed until the next time scheduled dose, if applicable. A parenteral formulation of the study drug will be provided for subjects in age groups C and D. Subjects randomized to receive placebo in the double-blind multiple-dose phase will be administered an oral liquid or parenteral formulation (depending on age group) that is identical in appearance to the active study drug.

The selection and timing of drug dosing will be as presented in Table 3 and Table 4 (Schedule of Events).

Following surgery, when subjects in Groups A and B are showing signs of tolerating oral intake and Subjects in Group C and D are showing signs of awakening and arousal their SOC postoperative analgesic regimen will be discontinued. All subjects will then be closely monitored for pain (pain scores will be recorded at least hourly) and they will be administered study drug or placebo once their pain score is ≥ 4 on the FLACC or ≥ 3 on the NIPS (day 1 time zero). Subjects in Groups A and B must be able to tolerate oral intake prior to receiving oxymorphone oral liquid. Background morphine-NCA (section 8.1.4) will be initiated coincident with study drug/placebo administration. No food or oral liquid restrictions will be imposed around the time of dosing. All subjects will receive morphine-NCA rescue as needed. The study drug will be administered every 4 to 6 hours as needed (q4-6h PRN) in the double-blind multiple-dose phase. Following dose 1, subsequent doses should be administered no less than 4 hours apart, and at least 20 minutes have elapsed since the last bolus NCA rescue. The last dose of study drug will be administered no later than 18h post first dose. All subjects must receive a minimum of 3 doses of study drug in the multiple-dose phase.

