9.3.1. Replacement of Subjects

9.3.1.1. Single-dose Phase

In the single-dose phase, up to 3 dose cohorts of 5 subjects may be studied (doses to be determined by IDMC) for each age group (see Table 7). Enrollment in each cohort will continue until at least 5 evaluable subjects are completed. To be considered an evaluable subject, each subject must meet the following criteria:

1. Receive expected dose of study drug
2. Complete at least 4 hours of post-dose assessments
3. Complete at least 3 PK assessments

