- Antidepressant therapy (excluding MAOIs) will remain stable (unchanged dose [$\pm 10\%$] and dosing regimen) throughout the study.

Constipation is the most common opioid AE. Laxatives should be used at the Investigator's, or designee's, discretion during treatment with study drug and recorded as a concomitant medication.

Nausea and vomiting are common opioid-induced AEs. It is expected that some of the subjects will need to be administered an antiemetic. Any antiemetic used during treatment with study drug should be recorded as a concomitant medication.

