14.6.2. Study Drug Exposure

During the single-dose phase, each subject will receive only 1 dose of the study medication. During the multiple-dose phase, the number of doses and cumulative dose received by each subject will be summarized by treatment, age group and overall.

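### The single-dose PK population keeps Group A and B infants who took only part of the oral dose, although the replacement rule treats them as non-evaluable; Cmax and AUC are biased low.

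*Protocol*

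**What the plan says.** Four parts of the protocol bear on this.

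- **Analysis set (14.2.1.1, same in the synopsis):** "The single-dose PK population will include all subjects who receive oxymorphone HCl (immediate-release oral liquid or IV formulation) and provide sufficient data points" for the non-compartmental calculation. The number of points that is enough is not defined, and nothing is said about the amount taken.
- **Replacement (9.3.1.1):** "Enrollment in each cohort will continue until at least 5 evaluable subjects are completed". The first of three conditions for being evaluable is "Receive expected dose of study drug"; the others are at least 4 hours of assessments and at least 3 PK assessments.
- **Incomplete oral doses (8.3):** "If a subject in groups A or B does not consume the entire dose, the subject should not be redosed" before the next scheduled dose. In the single-dose phase no next dose exists, because "each subject will receive only 1 dose of the study medication" (14.6.2).
- **Calculation (14.7.1, 14.7.2):** Cmax, Tmax, AUC, half-life, clearance and volume are estimated by standard non-compartmental methods and summarised by age group. Table 11 explains CL only as clearance and does not say whether the assigned or the administered dose is used. There is no rule for partial doses.

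The evaluable population in 14.2.1.1 also omits the dose criterion. It asks for at least one dose and that subjects "provide a minimum of 4 hours of post-dose assessments and at least 3 PK assessments to facilitate the dose selection decision". The SAP (3.15, 7.10 and 8) removes all PK analysis from the abbreviated report.

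**The concern.** The protocol recognises that some infants will not swallow the whole oral dose, and its replacement rule treats those infants as uninformative about that dose. The PK population does not follow that logic. An infant who spat out part of the dose triggers a replacement and then sits in the same table as the replacement, labelled with a dose that was not fully taken.

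Cohorts are small, so one such profile can visibly move a mean. Section 8.2.1 sends each cohort's efficacy, safety, tolerability and PK data to the IDMC for its next dose recommendation. Group A data inform the Group B starting dose, and modelling of Groups A and B informs the first IV dose in Group C (8.2, 8.2.1). Section 6.4.1 describes the younger infants as more at risk. A bias that makes a dose look less exposed than it is would be an unwelcome one to build into those data.

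**Working it through.** **Step 1: trace one infant through the rules.** Take a Group A infant who swallows part of the single dose and gives a full set of blood samples.

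| Rule | Outcome |
|---|---|
| 8.3, redosing | None; there is no later dose |
| 9.3.1.1, evaluable for replacement | No; expected dose not received, so enrolment continues |
| 14.2.1.1, evaluable population | Yes, with 4 hours of assessments and 3 PK assessments |
| 14.2.1.1, single-dose PK population | Yes, if the samples are sufficient |
| 14.7, dose correction | None stated |

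The infant is replaced and also analysed. This reads the expected dose as the full assigned dose, which is the natural reading beside 8.3.

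**Step 2: direction.** Assume linear PK and let f be the fraction of the nominal dose D that is retained. AUC and Cmax are multiplied by f. If clearance is computed as D/AUC with D nominal, apparent clearance is multiplied by 1/f.

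**Step 3: size in one cohort.** Section 9.3.1.1 gives five full-dose infants; add one partial-dose infant and treat all six as otherwise equal.

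- Arithmetic mean AUC or Cmax ratio = (5 + f)/6
- Geometric mean AUC or Cmax ratio = f^(1/6)
- Arithmetic mean CL ratio, nominal dose = (5 + 1/f)/6

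For f = 0.5: 5.5/6 = 0.917; 0.5^(1/6) = 0.891; 7/6 = 1.167.

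| f (assumed) | Mean AUC or Cmax | Geometric mean AUC or Cmax | Mean CL, nominal dose |
|---|---|---|---|
| 0.25 | 0.875 (-12.5%) | 0.794 (-21%) | 1.50 (+50%) |
| 0.50 | 0.917 (-8%) | 0.891 (-11%) | 1.17 (+17%) |
| 0.75 | 0.958 (-4%) | 0.953 (-5%) | 1.06 (+6%) |
| 0.90 | 0.983 (-2%) | 0.983 (-2%) | 1.02 (+2%) |

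**Step 4: size in the age-group table.** Section 14.7.2 summarises by age group, with up to 15 infants planned. With 15 full plus 1 partial at f = 0.5, and AUC dose-normalised or doses equal, mean AUC is 15.5/16 = 0.969 (-3%) and mean CL is (15 + 2)/16 = 1.06 (+6%).

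**Step 5: after the change.** With the dose criterion applied, only the five full-dose infants remain and every ratio is 1.00.

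The documents state no figure for incomplete doses that could be reproduced, so f and its frequency are assumptions throughout.

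**The case against.** Several points on the other side stand.

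- **Clearance.** A reader might take the upward bias in clearance as certain. It is not. Section 8.1.3 asks for medications to be recorded with the precise dose administered, and SAP 7.8.1 lists the volume given. If a partial amount is known and used, clearance is not biased by this route. Cmax and AUC still are.
- **Vomiting.** Section 10.2 says: "Nausea and vomiting are common opioid-induced AEs. It is expected that some of the subjects will need to be administered an antiemetic". A reader might infer that an infant who vomits early is likewise replaced and double-counted. An infant who swallowed everything and then vomited can satisfy the wording of 9.3.1.1, and nothing there provides for replacement. Inclusion criterion 10 also requires tolerance of clear liquids before oral dosing.
- **Larger figures.** Setting the partial infant among four full-dose infants gives -10%, -13% and +20% at f = 0.5. That does not match the replacement rule, which continues to five evaluable infants. It would apply only if the section 14 evaluable definition were used to stop enrolment.
- **Effect on dosing.** A reader might infer that the next dose would be set too high. The documents do not say that the IDMC sees only pooled summaries of this population, PK is one input among several, and the modelling for Group C falls under a separate population PK plan that is not available here.
- **Final report.** The SAP cancels the PK analysis, so no table in the abbreviated report changes.

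None of this closes the mismatch between 9.3.1.1 and 14.2.1.1, and no other section does so.

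**Conclusion.** The concern holds as an inconsistency in the protocol's planned non-compartmental analysis, limited to the oral Groups A and B. As written, a partly dosed infant with enough samples is replaced and still summarised, which lowers Cmax and AUC. Higher clearance follows only if the nominal dose is used, which is unstated.

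For one such infant added to a cohort of five, the bias in mean AUC runs from about 2% (f = 0.9) to 12.5% (f = 0.25), and it is about 3% in an age-group table of 16 at f = 0.5. These sizes rest on linear PK, otherwise equal infants and an assumed f. The documents do not show that any partial dose occurred.

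An influence on the IDMC's recommendation is a possible direction, not a demonstrated consequence. SAP 3.1.1 reports that the IDMC reviewed the first Group A cohort's data, including PK, so the rule mattered for data that were actually used even though the final PK analysis was dropped. The point merits correction in the protocol and in any later use of these concentrations.

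**What to change.** - **14.2.1.1 and synopsis, single-dose PK population.** For Groups A and B, add criterion 1 of 9.3.1.1 to the set used for the non-compartmental summaries. List the excluded infants' concentrations separately.
- **14.2.1.1 and synopsis, evaluable population.** Make the definition agree with 9.3.1.1, since it also omits the dose criterion.
- **14.7.1, Table 11, and the population PK plan.** State that clearance and the population PK dataset use the recorded administered dose where it is known, and that the profile is otherwise flagged or excluded. The population PK set in 14.2.1 has the same gap.
- **Vomiting after a full dose.** Prespecify how these profiles are handled in the analysis, for example by a sensitivity summary without them.

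The cost is a few sentences. Dose administered and AEs are already recorded; sites may also need to note the amount lost and the time of vomiting. The downside is occasionally one fewer non-compartmental profile. Replacement restores it for a partial dose but not for vomiting after a full dose, which is a reason to use a sensitivity summary there instead of exclusion.

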14.2.1.2. Multiple-dose Phase

The safety population for the multiple-dose phase will include all subjects who receive at least 1 dose of study drug or placebo. All safety analyses for the multiple-dose phase will be performed using this population and in all safety analyses, subjects will be attributed to the treatment that they actually received regardless of their assigned randomized treatment.

The intent-to-treat (ITT) population will include all randomized subjects who receive at least 1 dose of study drug during the multiple-dose phase and complete at least 1 post-dose pain intensity assessment. All efficacy analyses and demographic/baseline characterization will be performed using this population and in all efficacy analyses subjects will be attributed to the randomized treatment regardless of the treatment they actually receive.

The per-protocol (PP) population will include all subjects in ITT population who do not violate the protocol in any fundamental manner related to the evaluation of efficacy. This population will be used for supporting the primary efficacy analysis.

14.3. Subject Disposition

The number and percentage of subjects enrolled/randomized, completed, prematurely discontinued and reasons for premature discontinuation during treatment periods will be presented for each treatment/dose group and age group. Screen failures and the associated failure reasons will be tabulated.

The subject disposition will be summarized for single-dose and multiple-dose phases separately.

14.4. Demographics and Other Baseline Characteristics

Demographics and baseline characteristics of the subjects who participated in single-dose phase will be summarized by age group and dose group using single-dose phase safety population.

Demographics and baseline characteristics of the subjects who participated in multiple-dose phase will be summarized by age group and treatment group using ITT population.

The descriptive summaries will include frequency tables for all categorical variables and numbers, mean, standard deviation, minimum and maximum for all continuous variables.

14.5. Efficacy Analyses

The primary analysis of this study will compare the cumulative morphine demand via NCA during the multiple-dose phase. The null hypothesis is there is no difference between the 2 treatment groups; while the alternative hypothesis is that the treatments are different. The 2-sided significance level is 0.05.

The primary analysis will be performed on both ITT and PP populations, with ITT as the primary population. All other efficacy analyses will be performed on ITT population only.

14.5.1. Primary Efficacy Variable

The primary endpoint (cumulative morphine demand via NCA) will be analyzed using a mixed effect model with subject as random effect and treatment and age group as fixed effect. The least square means for each treatment group (active treatment and placebo groups) and the difference between the treatment groups (active vs. placebo) as well as their 95% CIs will be calculated.

In addition, the cumulative morphine demand via NCA will be summarized by treatment group and by treatment group and age group using N, mean, SD, minimum, median, and maximum.

The curves of the mean cumulative morphine demand via NCA over time by treatment group will be presented.

14.5.2. Secondary Efficacy Analysis

As the pain assessment, the FLACC (used for subjects between the ages of 6 months and 2 years) and the NIPS (used for subjects 0 to <6 months) will be measured after the first dose of study drug until EOT for both single-dose and multiple-dose phases.

The FLACC ranges from 0 to 10; while the NIPS ranges from 0 to 7. Before any statistical analysis, all NIPS assessments will be normalized in reference to FLACC by dividing by 7 and multiplying by 10.

For the single-dose phase, the pain assessment will be summarized descriptively by age group and dose group at each time point.

For the multiple-dose phase, the pain assessment will be summarized descriptively by treatment group and by treatment and age group at each time point. In addition, a mixed effects linear model with treatment and age group as fixed effect and subject as random effect will be used. The least squared means and 95% CIs will be calculated using this model for each treatment group and the difference between treatment groups.

Incidence of NCA rescue medication use and time to the first use of bolus rescue will be analyzed using logistic regression, and Cox models, respectively.

14.5.3. Supportive Analyses

The primary endpoint will be repeated based on the PP population as a supportive analysis.

14.6. Safety Analyses

Safety variables include prior, concomitant, and follow-up medications, study drug exposure, treatment compliance, AEs, laboratory parameters, vital signs, and physical examinations, as well as respiratory and neurological assessments. For each safety parameter, the last assessment made prior to the first dose of study drug will be used as the baseline for all analyses of that safety parameter.

14.6.1. Prior, Concomitant, and Follow-up Medication

Prior, concomitant, and follow-up medication use will be summarized using the number and percentage of subjects by dose and age group for the single-dose phase and treatment for the multiple-dose phase.

14.6.2. Study Drug Exposure

During the single-dose phase, each subject will receive only 1 dose of the study medication. During the multiple-dose phase, the number of doses and cumulative dose received by each subject will be summarized by treatment, age group and overall.

14.6.3. Adverse Events

The Medical Dictionary for Regulatory Activities (MedDRA) will be used to code AEs.

An AE (classified by preferred term) that started during the treatment period will be considered a TEAE if it was not present prior to the first dose of study drug, or was present prior to the first dose of study drug but increased in intensity during the treatment period. If more than 1 AE is reported prior to the first dose of study drug and coded to the same preferred term, then the AE with the greatest intensity will be used as the benchmark for comparison to the AEs occurring during the treatment period which were also coded to that preferred term. Any AE present prior to the first dose of study drug that increases in intensity during the treatment period will be re-entered with a new start date of the date of increased intensity. An AE that occurs more than 14 days or 5 half-lives, whichever is longer, after the last dose of study drug will not be counted as a TEAE.

Descriptive statistics (the number and percentage) for subjects reporting TEAEs will be tabulated by system organ class and preferred term; by system organ class, preferred term, and severity; and by system organ class, preferred term, and relationship to study drug. If more than 1 AE is coded to the same preferred term for the same subject, the subject will be counted only once for that preferred term using the most severe and most related occurrence for the summarization by severity and by relationship to the study drug.

The distribution of TEAEs by severity and relationship to study drug will be summarized. SAEs and AEs leading to premature discontinuation of study drug will be summarized by preferred term and treatment group, and sorted by decreasing frequency for the test treatment. SAEs will be displayed separately for those events occurring before the first study drug dosing date and all subsequent ones.

These tabulations will be stratified by age group and dose group for the single-dose phase and treatment group for the multiple-dose phase.

Listings will be presented for subjects with SAEs, subjects with AEs leading to discontinuation, and subjects who die (if any).

